## 5.4 Data Collection and Tracking

The electronic data systems of the dialysis provider organizations contain detailed clinical information from every dialysis treatment and the results of laboratory tests and hospitalization dates. These data are maintained in central electronic data warehouses. For HiLo, a pre-specified subset of data elements will be extracted from the central data warehouses and securely (encrypted) transferred to the DCRI database at regular intervals. No laboratory studies will be performed specifically for the trial. The following data elements will be obtained from clinical care data for all trial participants at the indicated frequency:

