#### Hospitalizations data: all

#### Medications: all

All available data on medications will be made available to DCRI by electronic data transfer on a monthly basis, including but not limited to:

- Phosphate binders
- Activated vitamin D
- Home medications
- Calcium
- Calcimimmetics (oral and IV)

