## 8. STATISTICAL ANALYSIS PLAN AND DETERMINATION OF SAMPLE SIZE

## 8.1 Sample Size

The primary analysis of HiLo is the comparison of rank sum scores on the hierarchical composite endpoint of time to all-cause mortality and hospitalization rate. Simulations were employed to estimate the power of the planned analysis. The assumptions for the simulation include:

- 48-month study with a 24-month enrollment period
- Annual loss to follow-up rate of 5%
- 15% annual mortality rate in the standard of care arm and a hazard ratio of 0.85 comparing the intervention arm to the standard of care arm
- 35% of participants are "non-susceptible" to hospitalizations (will not have any hospitalizations during the course of the study).
- In the susceptible population, an average of 1.8 hospitalizations per year in the standard of care arm and 1.53 hospitalizations per year in the intervention arm (15% difference).

1000 different study populations with 3800 participants were simulated under the above assumptions and analyzed using the planned analysis method. The power was estimated as the percentage of significant results out of the 1000. The results of the simulation provided an estimated power above 95%. Under these same assumptions, there would be at least 80% power to detect a treatment difference for both mortality and hospitalization when analyzed as separate endpoints. These results indicate that the trial will have sufficient power to detect a treatment effect with a population size of 3800 participants.

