1.3 Number of Patients

Sample size calculations

A simulation was performed in order to determine whether a sample size of 3800 provides sufficient power to reject the null hypothesis of no difference between the treatment arms in time to all cause death and number of hospitalizations.

The simulation population was created under the following parameters:

- 1:1 randomization
- For each participant, administrative censoring occurs uniformly randomly between 2 to 4 years
- Annual loss to follow up rate of 5% (for example, due to kidney transplantation, change in dialysis modality, withdrawal due to participant choice, etc.)
- Annual mortality rate of 15% in the Lo treatment arm vs. 12.8% in the Hi treatment arm.
- An average of 35% of the study population are not susceptible to hospitalization and have no chance of experiencing a hospitalization during the course of the study (zero-inflated distribution of hospitalization)
- The remaining susceptible population experiences an average a 2 hospitalizations per year in the Lo treatment arm vs. an average of 1.89 in the Hi treatment arm.

The above population was simulated across 1000 iterations. The simulated population and outcomes were analyzed using the methods described in protocol section 4.5.1. Power was estimated as the number of iterations with a p-value less than 0.05 divided by the total number of iterations.

The estimated power from the simulation indicate that a sample size of 3800 patients will have more than 95% power.

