4. ANALYSIS METHODS

4.1 General Principles

This analysis plan is intended to support the primary and main secondary manuscripts planned for the HiLo study. Analysis plans for other manuscripts will be provided in separate documents.

In addition to specific analyses and presentations that are detailed in the following sections, results will be summarized for continuous measures using descriptive statistics, including the number of patients, mean, standard deviation, median and range as appropriate. For categorical variables, counts and percentage per treatment group will be presented. Unless otherwise specified, all statistical tests will have a two-sided significance level of α =0.05.

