4.5.2 Analyses of the Secondary Endpoints

The hypothesis of the main secondary endpoint of time to all-cause death will be tested in the ITT population using a Cox Proportional Hazards model including phosphate target group as an explanatory factor. The hazard ratio and 95% CI for the high phosphate target versus the low phosphate target will be calculated from the estimated model parameters. If the confidence interval does not include 1, then the null hypothesis will be rejected.

The all-cause PPY hospitalization rates will be analyzed under the following hypotheses:

H₀:
$$\mu_H = \mu_L vs. H_1: \mu_H \neq \mu_L$$

Where μ_H and μ_L are the all-cause PPY hospitalization rates in the Hi and Lo treatment arms respectively. A two-sided 95% confidence interval for the difference in the cause-specific PPY hospitalization rates between the study arms will be estimated under normality assumptions. If confidence interval does not include 0, then the null hypothesis will be rejected.

For the continuous longitudinal outcomes (change from baseline in serum albumin and PCR), mixed effect models will be created to test the null hypothesis that the change of each measure

will not differ by treatment group. The phosphate target group and the baseline measure will be included as fixed effect covariates and study site will be included as a random effect covariate in the model.

Two covariance structures for this model will be considered: the compound symmetry structure (CS) and the auto-regressive(1) (AR1) structure. Each covariance structure will be compared using the Akaike information criterion (AIC) and the Bayesian information criterion (BIC). The structure that provides better results on the AIC and the BIC will be chosen for the final adjustment model.

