4.5.3 Additional Analyses

An adjusted analysis of the main secondary endpoints will be performed. The following adjustment variables will be included in the models:

- Age
- Sex
- Race
- Calculated BMI
- Cause of end-stage renal disease
- Vascular access type

The covariance structure for the model will be selected in the same manner as for the serum albumin and PCR analyses described in section 4.5.2.

An adjusted analysis of time to all-cause death will be performed by repeating the analysis of the endpoint described in section 4.5.2, but including the same adjustment variables listed for the adjusted analysis of the primary endpoint in the Cox model.

Similarly, the analyses for the serum albumin and PCR will be repeated including the same adjustment variables in their respective models.

The ratio of hospitalized days will be tested with the following hypotheses:

 $H_0: \mu_H = \mu_L vs. H_1: \mu_H \neq \mu_L$

Where μ_H and μ_L are the mean ratio of hospitalized days in the Hi and Lo treatment arms respectively. If the two-sided 95% confidence interval for the difference in the mean ratios does not include 0, then the null hypothesis will be rejected.

Under a previous HiLo protocol, cluster randomization at the site level occurred but otherwise participants were enrolled and participated in the study in a similar manner to the current protocol. If it is determined to be appropriate, the primary outcomes of the participants enrolled under the cluster randomization will be analyzed separately. Furthermore, the results of this analysis will be combined with the primary analysis detailed in this SAP using meta-analysis methods. Details of both the analysis of the cluster randomized data and the meta-analysis will be provided in a future version of this document.

Additional analyses concerning COVID-19

Additional analyses are planned to investigate and control for the potential effect of the COVID-19 outbreak on the other planned analyses. If the data are available to construct an endpoint as described in section 3.3, then the primary and secondary analyses will be repeated using only non-COVID-19 related deaths and hospitalizations as endpoint events. Patients experiencing a death attributed to COVID-19 will be censored at the time of death.

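### The hospitalization-rate comparison ignores hospitalization before consent and so gives up some precision

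*SAP*

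**What the plan says.** - **Endpoint.** SAP 3.2 defines a patient-level per-person-year (PPY) rate: a patient's hospitalizations divided by that patient's follow-up in years. It is a main secondary endpoint.
- **Test.** SAP 4.5.2: "A two-sided 95% confidence interval for the difference in the cause-specific PPY hospitalization rates between the study arms will be estimated under normality assumptions". No covariate enters. The sentence says cause-specific, but the hypotheses just above it concern the all-cause rate; I read it as all-cause.
- **Adjusted analysis.** SAP 4.5.3 plans one for the main secondary endpoints: "The following adjustment variables will be included in the models". The list is age, sex, race, BMI, cause of ESRD and vascular access type. COVID-19 status may be added. Earlier hospitalization is not listed, nor is it among the baseline variables in Protocol 5.4 or SAP 4.3.2.
- **Contrast.** The SAP 4.5.2 models for albumin and PCR include the baseline value of the measure.
- **Data.** Protocol 5.4 says that the providers' systems contain "the results of laboratory tests and hospitalization dates", and its list of elements to be transferred includes "Hospitalizations data: all". No look-back period is given.

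**The concern.** A patient's recent hospitalization record is the natural baseline for a hospitalization-rate outcome. The plan accepts adjustment for baseline on albumin and PCR, which rank lower, but does not apply it to the rate. Its own sample-size model has very uneven patients (SAP 1.3: "An average of 35% of the study population are not susceptible to hospitalization and have no chance of experiencing a hospitalization during the course of" …), with the rest averaging about 2 per year. If that unevenness was already present before consent, an earlier count carries information about the later rate, and leaving it out keeps variance in the comparison that could be removed. At stake is the interval width on a main secondary endpoint and, if the true effect is as small as SAP 1.3 supposes, some power.

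**Working it through.** **Inputs from the documents.** SAP 4.1: "all statistical tests will have a two-sided significance level of α =0.05". SAP 1.3: "1:1 randomization", N = 3800 (1900 per arm), administrative censoring uniform over 2 to 4 years, 5% annual loss, annual mortality 15% vs 12.8%, 65% susceptible, 2 vs 1.89 hospitalizations per year in susceptibles. Protocol 8.1: "1000 different study populations with 3800 participants were simulated", mortality hazard ratio 0.85, 1.8 vs 1.53 per year. Minimum time on dialysis before entry: 3 months (Protocol 4.3.2).

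**Assumptions not in the documents.** The look-back w (0.25, 0.5 or 1 year), and how far susceptibility before consent carries over into the study.

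**1. The plan's own figure.** Protocol 8.1 claims at least 80% power for hospitalization analyzed alone. Simulating its inputs gives 95% on patient-level PPY rates and 99.9% on arm totals over person-years. The claim reproduces.

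**2. Unadjusted test, SAP 1.3 inputs.** The expected difference is 0.65 × (2 − 1.89) = 0.0715. The simulated median SD of the patient-level rate is 1.4966 and the median SE is 0.0485. Simulated power is 27–30%. The normal approximation gives 0.0715/0.0485 = 1.47 and Φ(1.47 − 1.96) ≈ 31%, slightly high because very short follow-up inflates the SE in some trials (mean SE 0.0527).

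**3. Adjusted for the earlier count, full persistence.** Let X be the count in w years before consent, Poisson with mean 2w in susceptibles and zero otherwise. The average on-study rate in susceptibles is (2 + 1.89)/2 = 1.945. Then:

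- Cov(Y, X) = 1.945 × 2w × 0.65 × 0.35
- Var(X) = 0.65 × 2w + (2w)² × 0.65 × 0.35
- R² = Cov²/(Var(X) × 1.4966²), and the SE is multiplied by √(1 − R²)

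| Look-back | Cov | Var(X) | R² | SE factor |
|---|---|---|---|---|
| 3 months | 0.221 | 0.382 | 0.057 | 0.971 |
| 6 months | 0.442 | 0.878 | 0.100 | 0.949 |
| 12 months | 0.885 | 2.210 | 0.158 | 0.918 |

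Simulation agrees: the median SE goes from 0.0485 to 0.0472, 0.0461 and 0.0445, which is 3%, 5% and 8% smaller.

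**4. Any-admission indicator.** With q = 0.65 × (1 − e^(−2w)), Cov = 1.945 × 0.35 × q and Var = q(1 − q).

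| Look-back | q | R² | SE factor |
|---|---|---|---|
| 3 months | 0.256 | 0.071 | 0.964 |
| 6 months | 0.411 | 0.144 | 0.925 |
| 12 months | 0.562 | 0.265 | 0.857 |

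The indicator separates susceptible from non-susceptible patients better than a straight line in the count. Simulations using both terms gave an SE about 4%, 7% and 14–15% smaller. Steps 3 and 4 thus give the two ends of the range.

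**5. Power.** Across steps 3 and 4, simulated power rises from about 27–30% to 29–32% (3 months), 30–34% (6 months) and 33–39% (12 months). With 1000 runs the Monte Carlo error is about √(0.3 × 0.7/1000) = 1.4 points, so single-point differences mean little.

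**6. Half persistence.** If half of patients keep their status and the rest draw it afresh, the covariance halves and R² falls to a quarter. For the indicator, R² = 0.018, 0.036 and 0.066, so the SE is 1%, 2% and 3% smaller. Simulations gave 1–4% and power gains of about 1–3 points.

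**7. Protocol 8.1 inputs.** With the count alone the median SE goes from 0.0439 to 0.0429, 0.0421 and 0.0409 (2%, 4% and 7% smaller). Power moves from 95% to 96%.

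**8. For any other correlation ρ.** The SE factor is √(1 − ρ²): 0.980 at ρ = 0.2, 0.954 at 0.3, 0.917 at 0.4 and 0.866 at 0.5. The 12-month count in step 3 corresponds to ρ = √0.158 ≈ 0.40.

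**The case against.** The unadjusted difference is valid under randomization, and which covariates to add is partly a matter of preference. That stands, and it limits the point to efficiency.

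The data may not be there. Protocol 5.4 extracts a pre-specified subset and sets no look-back for hospitalizations. Eligibility guarantees only 3 months of dialysis, not necessarily with the same provider. That baseline laboratory values predate consent does not show that a year of admissions does. This also stands, so confirmation has to come first.

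The SAP defines non-susceptibility over the course of the study and says nothing about the period before it. Persistence is therefore my assumption, and with half persistence the gain is small. This stands, and it is why the result is a range.

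Under neither set of inputs does adjustment change the picture much. With the Protocol inputs, power is already high. With the SAP inputs, it stays well below 80% even with 12 months of history. Correct, but a narrower interval at almost no cost is still worth having.

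A reader might infer more than this from the omission:

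- **That the comparison is biased or its error rate inflated.** Nothing in the documents supports that.
- **That power rises from 40% to 52%.** That result, with a 12-month count, is for a rate weighted by person-time, which is not the SAP 3.2 endpoint.
- **That the primary rank-score test or a count model must change too.** Adjusting the rank scores adds an analysis for little gain, and a count model would normally estimate a ratio instead of the planned difference. Both are optional.

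**Conclusion.** The point holds as a modest, inexpensive gain in precision. The hospitalization-rate test is unadjusted, and hospitalization before consent is missing from the adjusted analysis, although the providers hold the dates and the SAP adjusts albumin and PCR for baseline. On the planned endpoint with the SAP 1.3 inputs, the SE reduction runs from about 1% (3 months of history, half persistence) to about 15% (12 months, full persistence, count and indicator). The upper end needs both a full year of provider history and a status that does not change. Adjustment does not bring the SAP 1.3 scenario to conventional power, and the different hospitalization assumptions in Protocol 8.1 and SAP 1.3 are a separate matter.

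**What to change.** 1. Confirm with the providers that the extract includes hospitalization dates before consent, and how far back.
2. In the SAP, define baseline hospitalization as the all-cause count divided by the months of available provider history, up to 12 months before consent, plus an indicator of any admission. Add a missing-history indicator, so that patients without history stay in the model under the no-imputation rule in SAP 5.3 and unknown history is not counted as zero.
3. In SAP 4.5.2, estimate the planned difference in PPY rates by linear regression on arm and these terms, with robust standard errors. The estimate remains a difference in rates. Report the unadjusted difference alongside, and state in advance that the adjusted one decides.
4. Add the same terms to the SAP 4.5.3 adjustment list.

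The cost is SAP wording, a few derived variables and one query to the providers; no new procedure or patient contact. The downside is that history will be short and noisy for recent dialysis starters, and short or absent for patients who came from another provider, which shrinks the gain. The covariates should be fixed before arm-level outcome data are seen, since the trial is open-label.

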4.5.3 Additional Analyses

An adjusted analysis of the main secondary endpoints will be performed. The following adjustment variables will be included in the models:

- Age
- Sex
- Race
- Calculated BMI
- Cause of end-stage renal disease
- Vascular access type

The covariance structure for the model will be selected in the same manner as for the serum albumin and PCR analyses described in section 4.5.2.

An adjusted analysis of time to all-cause death will be performed by repeating the analysis of the endpoint described in section 4.5.2, but including the same adjustment variables listed for the adjusted analysis of the primary endpoint in the Cox model.

Similarly, the analyses for the serum albumin and PCR will be repeated including the same adjustment variables in their respective models.

The ratio of hospitalized days will be tested with the following hypotheses:

 $H_0: \mu_H = \mu_L vs. H_1: \mu_H \neq \mu_L$

Where μ_H and μ_L are the mean ratio of hospitalized days in the Hi and Lo treatment arms respectively. If the two-sided 95% confidence interval for the difference in the mean ratios does not include 0, then the null hypothesis will be rejected.

Under a previous HiLo protocol, cluster randomization at the site level occurred but otherwise participants were enrolled and participated in the study in a similar manner to the current protocol. If it is determined to be appropriate, the primary outcomes of the participants enrolled under the cluster randomization will be analyzed separately. Furthermore, the results of this analysis will be combined with the primary analysis detailed in this SAP using meta-analysis methods. Details of both the analysis of the cluster randomized data and the meta-analysis will be provided in a future version of this document.

Additional analyses concerning COVID-19

Additional analyses are planned to investigate and control for the potential effect of the COVID-19 outbreak on the other planned analyses. If the data are available to construct an endpoint as described in section 3.3, then the primary and secondary analyses will be repeated using only non-COVID-19 related deaths and hospitalizations as endpoint events. Patients experiencing a death attributed to COVID-19 will be censored at the time of death.

If the data for the analyses described in the previous paragraph are not available, there may be other options to control for the possible confounding from COVID-19. If it is known whether an enrolled patient was infected by COVID-19 in the past or whether a patient was infected during follow-up, then patient level COVID-19 status will be used as a covariate in adjustment models using mixed models as described at the beginning of this section. Two adjustment models using COVID-19 infection status will be fit to the data: 1) a model using infection status as the only adjustment covariate 2) a repeat of the adjustment model described at the beginning of this section including infection status as an additional covariate.

COVID-19 infection may lead to patients being removed from the study site for an extended time period (e.g. extended hospitalization, transfer to non-study dialysis clinic designated for infected patients, etc.) In these cases, it is unlikely that patients that should be receiving a higher phosphate target will continue on that target and will be treated so as to reduce phosphate to the standard of care. If the date of a patient's transfer away from their study site or dietitian and the date of return are available, then there will be an additional analysis repeating the primary analysis disregarding events that occur while the patient is not receiving dialysis at the study site. If a death occurs during a period away from the study site, then the patient will be censored at the date of transfer away from the study site. Additionally, hospitalizations will not be compared using the count of hospitalizations. Instead, the analysis will use hospitalization rate calculated as the number of hospitalizations occurring while the patient is at study site divided by the time that the patient received dialysis at the study site.

All primary, secondary, and additional analyses will be repeated in the IR population.

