### 4.6 Intervention

Two phosphate titration protocols will be used that have the same "look and feel" as those used in practice in an effort to sustain a mean time-averaged difference in serum phosphate between the two arms of  $\geq 1 \text{ mg/dl}$ :

- 1. Low serum phosphate target that is consistent with current standard of care: The goal is to titrate and maintain serum phosphate to <5.5 mg/dl.
- Higher serum phosphate target that is the intervention strategy: The goal is to titrate and maintain serum phosphate to ≥6.5 mg/dl by setting a serum phosphate threshold >7.0 mg/dl when binders will be initiated, as has been done previously.

A mean serum phosphate of 4.8–5.2 is anticipated in the low arm and 6.5–6.8 in the high arm, as observed in two pilot clinical trials. Since serum phosphate is 4–7 mg/dl in most patients with ESRD,  $\geq$ 1 mg/dl difference equates with a  $\geq$ 33% difference within the modifiable range of time-averaged phosphate exposure. Specific binder choices will be relegated to the discretion of local providers based on local practice.

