## 8.5 Other Planned Secondary Analyses

As an alternative approach to analyzing the secondary outcome of hospitalization, the analysis will be repeated after substituting individual participants' total number of days spent in the hospital per total length of follow-up in HiLo. Additional secondary outcomes related to nutrition are change from baseline in serum albumin, and PCR. Mixed effect models will be used for all available longitudinal observations in the ITT population to compare change from baseline in these secondary continuous variables between the two arms. Supplemental analyses will consider the "as treated" sample.

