2. ANALYSIS POPULATIONS

2.1 Definition of Analysis Populations

2.1.1 Intention-To-Treat (ITT) Population

The ITT population will include all patients that have consented to participation in the study. The treatment arms in analyses in the ITT population will be the participant's assigned phosphate target arm, regardless of the participant's actual phosphate levels throughout the course of the trial. The ITT population will be used in the primary analysis of efficacy and all major secondary analyses.

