2.1.2 In Range (IR) Population

The aim of the IR population is to include the patients that have reached the targeted phosphate levels for the trial. Table 1 in section 4.4.1 below presents the "in range" phosphate range for each treatment arm. Phosphate levels will be measured on a monthly basis for each patient in the trial. Patients that are in range for 75% of their monthly phosphate measures will be included in the IR population.

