2.1.3 In Range 2 (IR2) Population

The IR2 population will be defined similarly to the IR population, except it will include patients that are in range for 50% of their monthly phosphate measures.

2.2 **Protocol Deviations**

Because this is a pragmatic trial intended to evaluate effectiveness of the phosphate targets under real-world conditions, protocol deviations will be limited to: 1) enrollment of individuals who do not meet eligibility criteria or provide informed consent, and 2) breaches of participant confidentiality. Deviations will be reported by the DCRI to the IRB.

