3. STUDY ENDPOINTS

3.1 Primary Endpoint

The primary outcome for HiLo is the hierarchical composite of: 1) time to all cause death followed by 2) number of all cause hospitalizations. The use of this endpoint will allow for simultaneous testing of both mortality and hospitalizations while prioritizing mortality as the more important health outcome to consider. Time zero for the time to all cause death portion of the endpoint will be the date of the first dialysis session after the patient has consented to participate in HiLo.

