4.4 Application of Study Treatment

4.4.1 Treatment Adherence

Serum phosphate will be monitored throughout the trial. Participants are anticipated to have phosphate levels measured at the site at least once per month. The participant monthly average phosphate level and the site level average of the patient average will be monitored for each site to ensure that the site assignment to a phosphate target has the intended effect of changing the patients' phosphate levels. The patient monthly average will be the average of all phosphate measures in a calendar month. The target ranges for patients and site average for each arm are provided in Table 1. Sites will be provided a listing of patient IDs of patients falling outside of the "In range" range will be provided monthly.

Target phosphate (mg/dL)	Hi	Lo
In range	>6.5	<5.5
Near range	5.5 - 6.5	5.5 - 6.5
Out of range	<5.5	>6.5

Table 1. Phosphate target ranges for Hi and Lo arms.

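### The In Range population is defined from phosphate values inside the survival period, with no titration window or landmark, so analyses repeated in it can show a false mortality effect of unknown sign

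*SAP*

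**What the plan says.** SAP 2.1.2 gives the membership rule: "Patients that are in range for 75% of their monthly phosphate measures will be included in the IR population". The limits are in SAP 4.4.1, Table 1: above 6.5 mg/dL for Hi and below 5.5 mg/dL for Lo. No early months are set aside, no classification date is fixed, and no minimum number of values is required. SAP 2.1.3 defines a second set, IR2, in the same way, except that "it will include patients that are in range for 50% of their monthly phosphate measures".

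SAP 3.1 fixes the start of the survival clock: "Time zero for the time to all cause death portion of the endpoint will be the date of the first dialysis session after the patient" consents. Titration months are therefore part of follow-up.

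SAP 4.5.3 states that "All primary, secondary, and additional analyses will be repeated in the IR population". Those analyses carry decision rules: a p-value threshold in 4.5.1, and rejection when a confidence interval excludes 1 or 0 in 4.5.2 and 4.5.3. Nothing labels the IR repeats exploratory. No analysis is assigned to IR2.

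The confirmatory role lies elsewhere. SAP 2.1.1 says "The ITT population will be used in the primary analysis of efficacy and all major secondary analyses". Protocol 8.5 gives on-treatment work a secondary place: "Supplemental analyses will consider the" as-treated sample.

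On the two arms, Protocol 4.6 describes Lo as a "Low serum phosphate target that is consistent with current standard of care" and presents Hi as the intervention strategy.

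**The concern.** Membership is decided by values collected after randomization, during the same months in which deaths are counted. A patient who begins out of range must live long enough for later in-range months to outweigh the early ones. That waiting time is immortal: a death during it does not count against the IR group, because the patient never joins it.

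If the wait were equal in both arms, this distortion would largely cancel. The documents give reason to expect that it is not. Lo continues usual care, so many Lo patients may be in range at once, whereas Hi asks for a change from usual care. A longer average lag in Hi is plausible, and it would remove early deaths from Hi more than from Lo.

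Selection on achieved phosphate comes on top of this. IR keeps Hi patients with high values and Lo patients with low values. If phosphate level goes with prognosis, the two groups differ for reasons unrelated to assignment. At stake is a set of supplementary results, tested by the same rules as the main analyses, that could be taken for the effect among patients who achieved their target.

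**Working it through.** The documents give no figure for the IR population, so there is none to reproduce. All results below are under no mortality effect (true HR 1).

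**Inputs from the documents.** 75% rule (SAP 2.1.2); limits of 6.5 and 5.5 mg/dL (SAP Table 1); mortality 15% per year, used as a hazard of 0.15 in both arms; censoring uniform over 2 to 4 years; 5% annual loss (SAP 1.3); anticipated mean phosphate of 4.8–5.2 in Lo and 6.5–6.8 in Hi (Protocol 4.6).

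**Inputs assumed, because the documents do not give them.** Lag to target in each arm, baseline mean, between- and within-patient SDs, and any phosphate-death link.

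**Step 1: the waiting time.** With n monthly values, of which the first m are out of range and the rest in range, membership needs (n − m)/n ≥ 0.75, so n ≥ 4m. One early month out of range requires 4 months of values, three require 12, and six require 24. For IR2 the condition is n ≥ 2m.

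**Step 2: lag alone, by hand.** Let L be the immortal time in years and λ = 0.15 − ln(0.95) = 0.201. Mean follow-up after L is r = {1 − [e^(−λ(2−L)) − e^(−λ(4−L))]/(2λ)}/λ. The death rate in IR is 0.15 × r/(L + r). A Lo patient always in range needs one value (L = 1/12), so r = 2.187 and the factor is 2.187/2.271 = 0.963. For Hi, L = 4m/12:

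| m | r | r/(L + r) | Ratio to Lo | Cox HR, simulated |
|---|---|---|---|---|
| 1 | 2.044 | 0.860 | 0.89 | 0.89 |
| 2 | 1.841 | 0.734 | 0.76 | 0.75 |
| 3 | 1.624 | 0.619 | 0.64 | 0.63 |
| 6 | 0.878 | 0.305 | 0.32 | 0.30 |

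With equal lags the simulated HR is 1.00; with 3 months in Hi against 2 in Lo it is 0.83. The bias comes from the difference in lag. This step is an extreme case, because every Hi patient starts out of range and then stays in range.

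**Step 3: monthly values that vary.** Lo has mean 5.0 from the start, Hi rises from 5.3 to 6.65, and both SDs are 0.9:

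| Phosphate-death link (log-HR per between-patient SD) | 1-month ramp | 3-month | 6-month |
|---|---|---|---|
| none | 0.90 | 0.84 | 0.72 |
| +0.1 | 1.05 | 0.99 | 0.90 |
| +0.2 | 1.25 | 1.22 | 1.14 |

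Separate runs of this set-up differ by up to about 0.05. With no ramp and no link, HR is 1.01–1.06 for SDs of 0.8–1.0. With SD 0.9, no link and trial size 3,800, false-positive rates are 24%, 41% and 55% for 1-, 2- and 3-month ramps. About 23–33% of Hi and 45–50% of Lo qualify.

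**Step 4: a common baseline.** If both arms start at the same mean and ramp alike, with no link, HR is about 0.86–0.95 from 5.5 mg/dl, 0.99–1.02 from 5.8 and 1.04–1.11 from 6.0. The higher the starting level, the more of the lag falls on Lo.

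**Step 5: a landmark.** Classifying on months 3–8 and counting survival from the end of that window gives HR 0.97–1.04 with no link. With a link of +0.1 to +0.2, it gives 1.09–1.46. The landmark removes the timing bias but not the selection.

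**The case against.** The strongest reply is that the direction is not established. A reader might infer from the immortal-time argument that IR would show a Hi benefit whenever there is none. The documents do not support that. They give no titration time, baseline mean or SD. Protocol 4.3.2 has no phosphate criterion, so some Lo patients also start out of range. Protocol 1.1 and 6.1.2 report that high phosphate is associated with death, which pushes the IR comparison towards harm in Hi; Steps 3 and 4 show that this link or a baseline near 6.0 removes or reverses the benefit. A link the other way would enlarge it: −0.2 per SD with a 3-month titration gave HR 0.61 under slightly different settings. This part of the objection stands in full.

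A reader might also infer that early Hi deaths cannot enter IR at all. That is true only of patients who start out of range. Protocol 4.6 puts most patients at 4–7 mg/dl, so some exceed 6.5 at once. In the Step 3 set-up without a link, 14–24% of first-year Hi deaths do enter, against 23–29% of all Hi patients. Early Lo deaths above target are also excluded.

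Finally, ITT carries the primary and major secondary analyses, so no confirmatory conclusion rests on IR. That stands and limits the weight of the point. It does not repair the rule: an analysis that can return a false benefit or a false harm, depending on unknown inputs, is not informative about patients who reached target.

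**Conclusion.** The point holds as a defect of a supplementary analysis. The documents alone establish that IR membership depends on post-randomization values within the survival period, that nothing allows for titration, and that every analysis is repeated in IR under the same rejection rules. The 4m-month requirement is exact for patients who start with m out-of-range months.

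The size rests on assumptions. If Hi lags Lo, Lo starts at target and phosphate is unrelated to death, the null HR is roughly 0.72–0.90, which spans the HR of 0.85 that Protocol 8.1 plans to detect. Other plausible inputs give no bias, or about 1.1–1.3. Neither sign nor size can be fixed from the documents.

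The figures cover the Cox analysis of death only. The hierarchical endpoint, hospitalization, albumin and PCR were not simulated in IR.

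**What to change.** In SAP 2.1.2, define IR by a fixed window after titration, the same in both arms, with a minimum number of values in it. Classify only patients who are alive and in follow-up at the end of the window, and count deaths and hospitalizations from that date. The months 3–8 used above only illustrate this; the sponsor should set the window from its own titration procedures, before unblinded data are seen. Apply the same definition to IR2 in SAP 2.1.3 if it is to be analysed, or say that it will not be.

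In SAP 4.5.3, label the IR analyses exploratory, report estimates and intervals without rejecting null hypotheses, and state that the landmark removes the timing bias but leaves selection on post-randomization phosphate.

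The cost is SAP wording and reprogramming of a supplementary population. Events before the landmark are lost to this analysis only.
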